PROTOCOL AMENDMENT #3

LCCC 1614: The MOVES Trial: MOTiVating Endometrial Cancer Survivors with Activity Monitors and Tailored Feedback

AMENDMENT INCORPORATES (check all that apply):

Editorial, administrative changes
 Scientific changes (IRB approval)
 Therapy changes (IRB approval)
 Eligibility Changes (IRB approval)

AMENDMENT RATIONALE AND SUMMARY:

This amendment increases the accrual from 36 to 39 participants to account for participants who did not complete the study and ensure enough evaluable data is collected to meet the aims of the study.

1. We updated Section 1.1 to justify accrual from 36 to 39 patients.
2. Section 4.0 graphics was updated to show new accrual goal.
3. Section 5.0 was also updated to justify new accrual goal
4. We are changing the PI from [name] MD to [name] MD

PROTOCOL AMENDMENT #2

LCCC 1614: The MOVES Trial: MOTiVating Endometrial Cancer Survivors with Activity Monitors and Tailored Feedback

AMENDMENT INCORPORATES (check all that apply):

Editorial, administrative changes
 Scientific changes (IRB approval)
 Therapy changes (IRB approval)
 Eligibility Changes (IRB approval)

AMENDMENT RATIONALE AND SUMMARY:

This amendment adjusts timing of consent and enrollment visits to minimize the time lapse in between these two occurrences (~3 months). After careful review, waiting about three months between consent and enrollment can askew data and cause patient behavioral changes.

1. Edited exclusion criteria in section 3.2.2 to exclude patients with no computers or Bluetooth capabilities as those are required for the study.
2. Edited schema in section 4.1 and changed “Day on enrollment” to “Baseline Visit”
3. Edited section 4.2 to include:
 - a. The possibility of contacting physician-identified patient’s via telephone to assess interest and obtain verbal consent.
 - b. In-person interactions will now allow coordinator to approach possible subjects to introduce the study prior to consent
 - c. A third phone call to remind patient of fasting prior to the post-intervention visit
 - d. Clarification that all subjects will now receive reminder emails to sync Fitbit and log into UNC CHART
4. Edited section 4.3 to reflect re-adjustment of timing of consent & enrollment visits so these can occur on the same day.
5. Removed mentions of GPAQ show cards and Appendix 2 and 3 in the protocol (section 4.3 and section 5.1)

PROTOCOL AMENDMENT #1

LCCC 1614: The MOVES Trial: MOTiVating Endometrial Cancer Survivors with Activity Monitors and Tailored Feedback

AMENDMENT INCORPORATES (check all that apply):

Editorial, administrative changes
 Scientific changes (IRB approval)
 Therapy changes (IRB approval)
 Eligibility Changes (IRB approval)

AMENDMENT RATIONALE AND SUMMARY:

This amendment adjusts timing of consent and enrollment visits to ensure study coordinators can approach subjects at standard of care visits and call subjects prior to day of eligibility and enrollment to the study. This amendment also alters eligibility criteria to exclude those with documented medical conditions, which would limit a subject's physical activity. The six-minute walk test is excluded, as it is not practical to conduct in the gynecology oncology clinic.

1. Edited exploratory objective 2.2.1 for clarity
2. Deleted previous inclusion criteria 3.1.5 describing the 6-minute walk test.
3. Added inclusion criteria 3.1.5 requesting approval from treating physician to engage in physical activity
4. Added inclusion criteria 3.1.6 and 3.1.7 to include patients having smart phones with Bluetooth capabilities and access to email
5. Edited exclusion criteria 3.2.4 and 3.2.5
6. Added exclusion criteria 3.2.6
7. Edited schema in section 4.1
8. Edited timeline of events in section 4.1
9. Edited section 4.2 Duration of Study to reflect adjusted timing of consent.
10. Added email reminders in section 4.2
11. Edited 4.3 Study Details to reflect new timing of consent
12. Edited 4.4.4 to include language about UNC CHART
13. Edited section 5.1 time and events table to reflect new timing of consent
14. Deleted erroneous randomization details in 7.1 Study Design
15. Edited sections 8.3 and 8.4.2 to reflect new Lineberger Comprehensive Cancer Center policies
16. Removed appendices 2-6 on section 10.0

LINEBERGER COMPREHENSIVE CANCER CENTER
CLINICAL ONCOLOGY RESEARCH PROGRAM
UNIVERSITY OF NORTH CAROLINA AT CHAPEL HILL

LCCC 1614: The MOVES Trial: MOTiVating Endometrial Cancer Survivors with Activity Monitors and Tailored Feedback

Principal Investigator(s):

[name], PhD
Division of Gynecologic Oncology
University of North Carolina at Chapel Hill
[contact] (phone)
[contact] (fax)
Email: [contact]

Co-Investigators:

1.0 BACKGROUND AND RATIONALE

1.1 Study Synopsis

Overweight and obese endometrial cancer (EC) survivors at UNC-CH will be approached for tailored feedback fitness intervention. We aim to enroll 36 evaluable women (18 in each arm) to evaluate if receipt of weekly tailored feedback messages can improve physical activity in EC survivors. We anticipate enrolling 39 participants to be able to evaluate 36. We hypothesize women receiving the feedback message intervention will increase step counts from baseline more than 2,000 steps compared to women in the non-intervention arm.

1.2 Background

In 2016, approximately 60,050 new cases of EC will be diagnosed with 10,470 women dying from EC (1). EC incidence in the United States has been increasing largely due to a combination of an aging population and increasing adolescent and adult obesity. In our recent multi-institutional analysis of 1400 EC patients treated over 5 years, 66% of our EC patients were obese, and 85% were overweight/obese (2). Obesity, diabetes, and insulin resistance contribute to the development of EC through hormonal alterations resulting in an estrogen dominant state, as well as through hyperinsulinemia and elevated serum glucose levels causing increased cellular proliferation and tumor growth (3-5). In addition to driving cancer development, obesity is associated with an increased risk of death in EC patients (6-9). Morbidly obese women with EC have a 6.25-fold increased risk of death from EC as compared to their non-obese counterparts (7). Fortunately, many ECs are diagnosed at an early stage and able to be fully treated via hysterectomy +/- radiation. As a result, three years following their diagnosis, EC patients are more likely to die from cardiovascular causes due to significant medical co-morbidities than from EC (10).

EC Survivor Knowledge and Readiness. Given the strong relationship between EC and obesity, we recently conducted a survey study of EC survivors to assess their knowledge of the relationship between EC and obesity (11). We found that only 46% of responders knew of the link between obesity and EC. There is evidence to suggest that the time of cancer diagnosis represents a “teachable moment” where patients are more motivated to make behavioral change (12, 13). Indeed, we found that majority (70%) of women desired to live a healthier lifestyle after their EC diagnosis (11). Despite this reported desire, only 52% of patients attempted weight loss and only 48% of patients attempted to increase physical activity. Survivors who did not attempt weight loss cited a lack of time, money or knowledge of how to lose weight. Survivors were most likely to attempt behavioral change 3 to 6 months following their diagnosis.

Physical Activity and Weight Loss. Weight loss is attained through a combination of physical activity and diet. Specifically, an individual must increase one’s metabolic expenditure and reduce caloric intake in order to maintain weight loss. Modest sustained weight loss of approximately 10 kg has been shown to result in improved health outcomes (14). While both diet and physical activity are critical to sustained weight loss, physical activity appears to be particularly important to improving cardiovascular health. In fact, increasing levels of physical activity and fitness have been shown to have health benefits, even in the absence of weight loss in obese patients (15, 16). Further, increasing physical activity by 2000 steps per day (or a 20 minute walk at moderate pace) is associated with a 10% reduction in long-term cardiovascular events (defined as cardiovascular mortality, stroke, or myocardial infarction) (17). Thus, in EC survivors with significant risk of cardiovascular mortality, we will focus on increasing physical activity as the primary intervention of our study.

Activity Trackers and Physical Activity. It has been well reported that step-based physical activity programs can effectively and safely increase physical activity in sedentary individuals (18-20). Activity trackers represent the ideal accelerometer as they can track steps, calories, heart rate, and other parameters overtime that can be used by researchers or providers to monitor activity through web-based interfaces. Further, activity trackers have the added advantage of allowing women to perform self-monitoring of their behavior change, which has been shown to be more effective in similar populations (21-23).

CHART and Tailored Feedback. The Carolina Health Assessment and Resource Tool or CHART has been successfully utilized in a variety of settings to facilitate behavior change. CHART has available modules for wearable activity trackers, physical activity and weight. The modules provide users with individual assessment and tailored feedback to promote behavior change. Further, the CHART wearables module has been applied effectively to provide weekly tailored feedback in both AA men (iMOVEIt) and childcare providers (CARE2bFit). Both studies showed improved self-monitoring compliance and modest changes in physical activity. Men using wearables had about 600 more steps per day, while women in the CARE2bfit program increased their MVPA by 60% (12 to 20 minutes per day) through the middle three weeks of the study, but decreased back to week 1 levels as the program concluded. This tool has not been previously evaluated in EC patients, who appear highly motivated following their cancer diagnosis. Thus, *we propose a physical activity intervention in the EC survivor population, using weekly tailored feedback to increase steps per day using a wearable activity tracker.*

1.3 Purpose and Rationale

Given that overweight and obese women diagnosed with EC are more likely to die from cardiovascular causes of death than from EC, weight loss and physical activity in the EC survivor population is critical. We have previously shown that EC survivors are motivated to make behavioral change following their cancer diagnosis, but have a low success rate of increasing physical activity and losing weight without intervention. Tailored feedback interventions have been shown to be helpful in motivating behavioral change in other populations. Thus, *we propose a tailored feedback and activity tracker intervention to increase physical activity in EC survivors.*

2.0 STUDY OBJECTIVES AND ENDPOINTS

2.1 Primary Objective:

To assess if a tailored feedback fitness intervention can increase physical activity in EC survivors from baseline to 12 weeks post-baseline.

2.2 Exploratory Objective(s):

- 2.2.1 To determine the acceptability of the fitness intervention in EC survivors through completion survey.
- 2.2.2 To assess if a tailored feedback message fitness intervention can (1) decrease BMI, (2) reduce waist to hip (W/H) ratios, (3) improve quality of life (QOL) and (4) improve serum metabolic markers (insulin, glucose, and low-density lipoprotein (LDL) levels) in EC survivors.

3.0 PATIENT ELIGIBILITY

3.1 Inclusion Criteria

To participate in this study, all subjects will:

[figure not shown]
- 3.1.1** Be over the age of 18 years
- 3.1.2** Have a confirmed diagnosis of endometrial cancer and have completed therapy (surgery, chemotherapy or radiation) within the past 6 months
- 3.1.3** Have no current evidence of endometrial cancer
- 3.1.4** Have a BMI 25 kg/m² or greater
- 3.1.5** Have approval from their treating physician to engage in moderate-intensity physical activity.
- 3.1.6** Have a smart phone with Bluetooth capabilities turned on
- 3.1.7** Have access to email

3.2 Exclusion Criteria

Individuals will be excluded from this study if they:

- 3.2.1** Are currently undergoing treatment for their cancer
- 3.2.2** Are unable to read a sample message aloud
- 3.2.3** Do not have a computer or smart phone with Bluetooth capabilities
- 3.2.4** Are pregnant
- 3.2.5** Have a history of angina or palpitations with exertion
- 3.2.6** Have a history of uncontrolled pulmonary disease (COPD or asthma)
- 3.2.6** Have one or more significant medical conditions that in the physician's judgment preclude participation in the walking intervention.

4.0 STUDY PLAN

5.0 Schema

This is a randomized controlled pilot study of 39 total participants to ensure 36 evaluable datasets (n=18 per arm) of overweight or obese patients with endometrial cancer. The primary purpose of this study is to evaluate the change from baseline of daily steps in women randomized to the tailored feedback message fitness intervention. We anticipate a patient's active participation will last approximately 12 weeks.

5.1 Duration of Study

Patients enrolled in this study will participate for approximately 12 weeks. The participants will be consented at the end of their cancer treatment. The participant will remain on study until their next clinic visit (~3 months).

There will be up to three in-person interactions with the patients in this study: during a clinic visit where the study is introduced, on the day of the baseline visit, and at the time of their 3-month follow up or post-intervention visit. Patients will be approached by the study coordinator for participation in this study during routine clinic visits. If a provider identifies eligible patients in advance of their scheduled visit and notifies the study coordinator, the study coordinator will contact the patient via telephone prior to their clinic visit to introduce the study and assess interest. If the patient is interested, the study coordinator will obtain a telephone consent. At the next scheduled visit, the study coordinator will obtain the patient's signed consent and provide a physical hardcopy of their signed consent form to the patient prior to initiating any study activities.

There will also be three phone calls from the study team: prior to the baseline visit to remind the patient to fast for blood collection, at the end of week 1 to ensure successful use of the fitness tracker, and prior to the post-intervention visit to remind the patient to fast again. For all subjects, study staff plans to send out email reminders so they can sync their Fitbits in time and log into UNC CHART to ensure data quality.

5.2 Study Details

Women with endometrial cancer, at the end of cancer treatment, will be recruited from the Gynecologic Oncology clinic at UNC-CH (see inclusion/exclusion criteria above). The standard care of a woman diagnosed with endometrial cancer is to undergo treatment with hysterectomy followed by possible adjuvant radiation or chemotherapy in high risk or advanced stage cancer. Following completion of therapy, a patient is seen by her oncologist every 3 months in the first 2 years following treatment for cancer surveillance. We aim to identify women within 6 months of treatment completion, generally at the initial surveillance visit. Women meeting enrollment criteria will be approached for consent. Enrolled women will receive a Fitbit fitness tracker and be instructed in how to use UNC CHART. Study staff will spend time with each participant to help them access CHART, learn to see messages, and set-up and use of the fitness tracker. All participants will keep the fitness tracker after completion of the study as token of appreciation for their participation.

At the baseline visit, patient's baseline height and weight will be obtained. Blood pressure and baseline heart rate will also be documented. Baseline BMI will be calculated. In addition to BMI, the W/H ratio will be evaluated. The W/H ratio is defined as the waist circumference in centimeters divided by the hip circumference in centimeters. W/H may be a better predictor of cardiovascular morbidity than BMI as it takes into account abdominal adiposity (25). The proper technique for measurement of the waist and hip circumference is to have the subject stand with both feet together and arms at the side without bulky clothing. Measurements should be taken at the end of expiration and be repeated twice using stretch-resistant measuring tape. Both measurements should be within 1cm of each other and the average value used. The waist measurement is taken midway between the last palpable rib and the top of the iliac crest. The hip measurement is taken at the widest portion of the buttock with the tape parallel to the floor (26). W/H ratio at baseline will be calculated.

After the above measurements and vitals are taken, patients will complete an enrollment survey including the GPAQ survey to measure baseline activity and baseline FACT-G assessment (27, 28). Pre-intervention FACT-G total score and sub-scale scores (physical well-being, social well-being, emotional well-being and functional well-being) will be compared to post-intervention scores. Finally, baseline fasting glucose, insulin and LDL will be obtained at the time of study baseline activities. Blood and urine will be collected and stored for potential future metabolomic profiling. Patients will then be randomized to either receive or not receive tailored feedback messages through UNC CHART. Participants randomized to the message arm will begin receiving encouragement and reminder UNC CHART messages to increase physical activity weekly based on the CHART algorithm (Appendix 1). Participants on the feedback arm will receive 1 message per week during the 3-month study period.

For the first week after initiating the study, each patient's baseline step count will be obtained from the fitness tracker. The mean step count over these 7 days will represent the patient's baseline step count. After the baseline week is completed, the study team will contact patients to ensure successful use of technology.

At the time of next follow up visit, the patient will undergo repeat weight, height, waist circumference, and hip circumference assessment. Heart rate and blood pressure will also be recorded at the follow up visit. The patient will complete a post-intervention acceptability survey and complete a post-intervention FACT-G assessment. Post-intervention fasting glucose, insulin, and LDL will be performed. Urine and blood will also be banked via the Tissue Procurement Facility (TPF) at the Lineberger Comprehensive Cancer Center (LCCC) for future metabolomic profiling.

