8.3 Data Analysis Plans

Our primary objective will be measured by comparing patients baseline step counts (defined as the mean step count recorded by the fitness tracker for each participant in the first 7 days following enrollment) to week 12 (final week of study participation) step counts. The week 12 step counts will also be the mean step count recorded by the fitness tracker over 7 days in a participant's final week on the study. The

mean change in steps in the intervention group will be compared to the no-intervention group using a Wilcoxon Two-sample test.

For our exploratory objectives:

Acceptability of the intervention will be measured, as previously reported, using the results of a post-intervention Likert scale survey (29). At study conclusion, patients randomized to the feedback messaging arm will complete a post-intervention survey regarding the acceptability of the invention. Question #1 of the post-intervention survey will ask patients about the acceptability of the intervention using a 5-point Likert scale. The completion survey will also include information about desired frequency of messages, desired content of messages, and timing of messages. The information obtained in this portion of the study will allow improvements to be made in our intervention prior to implementation of a larger randomized trial. The acceptability of the intervention will be defined as the proportion of patients answering favorably (very helpful or somewhat helpful) to question #1 on the completion survey. We aim to have 80% acceptability. Previous surveys of adults have shown 81% to find mobile health interventions acceptable (34). We will report the proportion of subjects reporting favorable responses to question #1 on the completion survey and the corresponding 95% CI.

Finally, we will look for decrease in BMI, improved W/H ratio, improved QOL, and improved serum metabolic markers. These data will be preliminarily evaluated in this pilot study, but will represent the primary endpoints of interest in the randomized trial to be conducted following completion of this pilot. Basic descriptive and comparative statistics will be performed to evaluate BMI, QOL, W/H ratio and insulin/glucose/LDL levels as exploratory endpoints at each time point, in addition to the change in each exploratory endpoint between time points. All computed descriptive statistics would be stratified by study arm.

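### The step baseline of the primary change score is recorded after randomisation with no masking or delayed disclosure described, so a week-1 reaction to knowing the arm would be subtracted from the effect; its size and sign are unknown

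*Combined protocol and SAP*

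**What the plan says.** Section 5.2 (Study Details) gives the order of events. At the baseline visit, weight, height, waist and hip are measured, then "patients will complete an enrollment survey including the GPAQ survey to measure baseline activity" and FACT-G, and fasting bloods are drawn. The next step is: "Patients will then be randomized to either receive or not receive tailored feedback messages through UNC CHART".

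The step baseline comes from the tracker in the first week on study: "The mean step count over these 7 days will represent" the baseline. Section 8.3 uses the same quantity in the primary endpoint, "defined as the mean step count recorded by the fitness tracker for each participant in the first 7 days following enrollment", and compares it with the 7-day mean of week 12. The events table in section 6.1 labels week 1 as the baseline for step monitoring.

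On contact and messages:
- Section 5.2: "After the baseline week is completed, the study team will contact patients to ensure successful use of technology". Section 5.1 places this call at the end of week 1.
- Section 6.1 schedules messages for the feedback arm in weeks 2 to 12.
- Section 5.2 is looser: "Participants on the feedback arm will receive 1 message per week during the 3-month study period".

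The only statement on blinding (section 5.3.4) concerns research IDs on data and specimens. Section 5.4 recognises a Hawthorne effect, but only from repeated phone calls in weeks 2 to 12.

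**The concern.** Weight, waist and hip, questionnaires and bloods are all taken before allocation, so randomisation balances them apart from chance. The step baseline is not protected in this way, because it is measured in the week after allocation. A woman who knows she will receive feedback might walk more from the first day. A woman who knows she will not might do the same to compensate, or might lose interest. The change score treats any resulting arm difference in week 1 as habitual activity and removes it from the week-12 result.

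A higher feedback-arm baseline would dilute the estimate and a higher control-arm baseline would inflate it, so the design cannot be called conservative. Adjusting for the week-1 value would not repair this, because that value is itself measured after randomisation. A reaction common to both arms, for example to wearing a tracker, cancels and is not at issue.

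**Working it through.** **1. The plan's own figure.** Inputs from section 8.2: difference 2000 steps/day, change-score SD 1800, two-sided alpha 0.05, Wilcoxon two-sample test, 15 women (read as per arm), 80% power. Method: noncentral t with n multiplied by the Wilcoxon efficiency 3/π for normal data.

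- n = 15: effective n = 15 × 3/π = 14.32; noncentrality = (2000/1800) × √(14.32/2) = 2.97; power 81.7%. Simulating the exact test gives 80.2%. The plan's figure is reproduced.
- n = 18, the evaluable target: effective n = 17.19; noncentrality = (2000/1800) × √(17.19/2) = 3.26; power 88.5%.

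**2. Bias.** Let M be the week-12 arm difference due to the messages alone, r the week-1 arm difference (feedback minus control) caused by knowing the arm, and p the share of r still present at week 12.

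- Week-12 difference = M + pr
- Change-score contrast = M + pr − r = M − r(1 − p)
- If the target is the messages alone (M), bias = −r(1 − p): only the part that fades.
- If the target is the total effect of assignment (M + pr), bias = −r: the whole week-1 difference.

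Section 1.1 states the aim as "to evaluate if receipt of weekly tailored feedback messages can improve physical activity in EC survivors", which points towards the first target but does not settle it. With M = 2000 and r = 500 (assumed):

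| p | Contrast | Bias, messages alone | Bias, total effect |
|---|---|---|---|
| 0 | 1500 | −500 | −500 |
| 0.5 | 1750 | −250 | −500 |
| 1 | 2000 | 0 | −500 |

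**3. Illustration.** The documents give no value for r, so 250 and 500 are assumptions. The reaction is taken as fully faded (p = 0), where the two targets coincide. SD 1800, 18 per arm.

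| Case | Contrast | Noncentrality | Rejection rate |
|---|---|---|---|
| True effect 2000, no reaction | 2000 | 3.26 | 88.5% |
| True effect 2000, feedback-arm reaction 250 | 1750 | 2.85 | 79.0% |
| True effect 2000, feedback-arm reaction 500 | 1500 | 2.44 | 65.9% |
| No effect, control-arm reaction 250 | 250 | 0.41 | 6.8% |
| No effect, control-arm reaction 500 | 500 | 0.81 | 12.4% |

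Simulation of the exact test gives similar values: 78.1% and 64.8% for the two power cases with a reaction, and 6.4% and 11.6% for the two null cases.

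For scale, section 1.2 reports from an earlier CHART programme: "Men using wearables had about 600 more steps per day". A shift of 500 from learning the allocation alone would therefore be large.

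**4. Could the week-1 data show it?** The standard error of the week-1 arm difference is 1800 × √(2/18) = 600, with SD 1800 taken from the upper end of the range for daily steps in section 8.2. The 95% half-width is 2.03 × 600, about 1220 steps. A 500-step shift could not be excluded.

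**5. Message start.** Section 6.1 gives weeks 2 to 12, which is 11 weeks. The feedback table in Appendix 1 has reports for weeks 1 to 11, each built from the previous 7 days, so it is consistent with section 6.1. The wording in section 5.2 does not exclude a message in week 1.

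**The case against.** The strongest reply is that the mechanism rests on silence. The protocol does not say that women are told their arm before week 1. In that week both arms get the same tracker, the same CHART training and the same reminder emails, so nothing described would reveal the arm unless staff disclose it. What women are told may also be in consent text that was not available for review. All of this stands. A reader might infer that women know their arm in week 1 and that the baseline is therefore contaminated, but the documents support only the weaker statement that nothing described prevents it.

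A reader might also infer from the looser wording in section 5.2 that messages reach the feedback arm during the baseline week. The events table and Appendix 1 point the other way, so the concern is a reaction to assignment, not to messages.

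Second, the size is assumed and the modest case does little harm: at 250 steps, power stays near the planned 80%, and this is a pilot. That also stands and lowers the priority.

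Third, Amendment 3 raises accrual because some participants did not complete, which suggests that most women may already be randomised. Re-ordering might then reach few of them and would mix two baseline procedures. This limits the first part of the fix but not the rest.

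**Conclusion.** The point holds in conditional form. The order of events is clear from section 5.2, although section 6.1 has no row for randomisation and section 8.3 counts from enrollment. The primary change score is therefore open to an arm-dependent reaction in week 1. The documents do not show that a reaction occurs, how large it is or which way it runs, so a claim that the result will be biased, or biased in a particular direction, is not supported.

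The power and rejection figures rest on an assumed reaction that has faded by week 12, normal data, SD 1800 and 18 women per arm. Where part of the reaction persists, the bias depends on which target the trial adopts. Priority is low to moderate: the consequence may be small, but the route can be closed for future participants at little cost.

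**What to change.** 1. **Women not yet randomised.** Keep the baseline visit and the tracker and CHART training. Randomise, or disclose the arm, at the existing end-of-week-1 contact, after the 7-day baseline has synced and before the first week-2 message. Flag these women in the analysis. Cost: an amendment, possibly an extra contact for late syncing, and fewer randomised from the 39 enrolled because women who stop in week 1 would not be allocated. No new visit is needed. Few women may remain to benefit.

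2. **All women.** Add a sensitivity analysis comparing week-12 mean steps between arms without subtracting week 1. State that it includes any persistent reaction to assignment and does not remove chance imbalance in habitual steps. Its power for 2000 steps is 88.5% if the week-12 SD is 1800, and 81.2% or 73.4% if that SD is 2000 or 2200 (assumed). Report week-1 steps by arm with a 95% CI as description only, given its imprecision. Both use data already planned.

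3. **Text.** State when women learn their arm, and say whether the target is the effect of the messages alone or the total effect of assignment. Reconcile the message start in section 5.2 with section 6.1. These are wording changes.
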